5.1 Randomization/Treatment Assignment

Subjects who meet all eligibility requirements ([Section 4.1](#)) will be randomly assigned in a 1:1 allocation ratio to the 2 treatment groups (romosozumab and placebo) in a double-blind manner.

Randomization will be based on a schedule prepared by the Amgen Central Randomization Group before the start of the study. Randomization will be performed by IVRS, and the randomization number will be provided through the IVRS. A subject may be randomized only once, and each randomization number will be assigned only once.

The randomization date is to be documented in the subject's medical record and on the enrollment CRF.

5.2 Site Personnel Access to Individual Treatment Assignments

The identity of IP assigned to subject numbers or to individual packages of IP will be contained in the IVRS. Authorized site staff will be provided with a unique Personal Identification Number to access the IVRS to obtain unblinding information. This Personal Identification Number is unique to the individual and must not be shared.

A subject's treatment assignment should only be unblinded when knowledge of the treatment is essential for the further management of the subject on this study.

Unblinding at the study site for any other reason will be considered a protocol deviation.

The investigator is strongly encouraged to contact the Amgen Clinical Study Manager before unblinding any subject's treatment assignment, but must do so within 1 working day after the event.

Refer to the Investigational Product Instruction Manual (IPIM) for instructions on how to access treatment information in the event the blind needs to be broken.

6. TREATMENT PROCEDURES

6.1 Classification of Products and Medical Device

The Amgen IPs used in this study are romosozumab and matching placebo. The IPIM, a document external to this protocol, contains detailed information regarding the storage, preparation, destruction, and administration of romosozumab and placebo.

The non-Amgen non-IPs used in this study are elemental calcium and vitamin D.

The medical device used in this study is a prefilled syringe (PFS).

6.2 Investigational Product

6.2.1 Amgen Investigational Product

Romosozumab and matching placebo will be manufactured and packaged by Amgen Inc. and distributed using Amgen clinical study drug distribution procedures.

Romosozumab will be supplied in a single-use PFS as a sterile, clear, colorless or slightly colored, and preservative-free solution for SC injection. Each PFS contains 70 mg of romosozumab per mL in C mM acetate and C mM calcium containing CCl % w/v sucrose and CCl % w/v polysorbate 20 at pH CC with a deliverable volume of 1 mL. The 3 romosozumab 70 mg/mL PFSs to be administered at each dosing visit will be packaged together in a single box.

Placebo will be presented in identical containers and stored/packaged the same as romosozumab.

6.2.1.1 Dosage, Administration, and Schedule

The IP will be administered in accordance with instructions in the IPIM.

The IP (romosozumab/placebo) will be administered SC via PFS on day 1, month 1, month 2, month 3, month 4, and month 5. All doses will be administered at the study site.

Subjects will receive 3 SC injections of romosozumab (ie, 3 injections of 70 mg romosozumab for a total dose of 210 mg) or matching placebo QM. A separate PFS will be used for each injection; however, all 3 PFS to be used at a specific visit will be supplied in a single box, as assigned by the IVRS.

Injections will be administered by a healthcare professional into different sites on the subject's anterior abdominal wall, upper thigh, or upper arm. The injection should not be administered in the same arm from which blood is drawn. The romosozumab/placebo SC injection must be administered as the last procedure after all other study visit procedures have been completed.

The volume, start date/time, each administration site, and box number of romosozumab/placebo are to be recorded on each subject's CRF.

A physician must be available during administration of romosozumab/placebo. It is recommended that all subjects be closely observed for approximately 30 minutes after dosing with IP.

The first dose of IP should be administered on the day of randomization. If this is not possible, it must be administered within 72 hours of randomization.

Refer to specific instructions provided by the IVRS vendor for additional information on box assignment and to the IPIM for additional information regarding storage and preparation of IP.

Overdose with this product has not been reported. The effects of overdose of this product are not known. An antidote to overdose of this product is not known. The maximum amount of romosozumab that can be safely administered in a single dose has not been determined, and there is currently insufficient information to draw any conclusions about the safety of doses higher than those studied in clinical trials. The highest single dose of romosozumab tested in clinical trials is 10 mg/kg SC. Subjects who have received higher than protocol-defined doses should be carefully monitored for adverse events.

6.2.1.2 Dosage Adjustments, Delays, Rules for Withholding or Restarting, Permanent Discontinuation

No dosing adjustments for romosozumab/placebo will be permitted.

All efforts should be made to administer romosozumab/placebo within the defined study visit windows (refer to [Section 7](#)). In case of an out-of-window visit, romosozumab/placebo can be administered within ± 2 weeks of the target visit date (ie, calculated from the day 1 visit as described in [Section 7](#)). If romosozumab/placebo cannot be administered within ± 2 weeks of the target visit date, the dose has to be considered missed.

6.2.2 Non-Amgen Non-investigational Products

The non-Amgen non-IPs (vitamin D and calcium) that are commercially available are not provided by Amgen. The investigator will be responsible for obtaining supplies of these protocol-required therapies and will be reimbursed for those supplies.

The dose, start date, stop date, and frequency for calcium and vitamin D are to be recorded on each subject's CRF. At screening, the investigator or designee will instruct subjects on daily calcium and vitamin D supplementation.

Additional details regarding the non-Amgen non-IPs are provided in the IPIM.

6.2.2.1 Calcium

Subjects will receive daily calcium supplementation orally from screening to EOS, which at a minimum should be in the range of 500 to 1 000 mg elemental calcium.

6.2.2.2 Vitamin D

Where available, vitamin D₃ preparations should be used; if vitamin D₃ is not available, use of vitamin D₂ preparations is acceptable.

Subjects will receive daily vitamin D supplementation orally from screening to EOS, which at a minimum should be in the range of 600 to 800 IU vitamin D. In addition, subjects with a serum 25 (OH) vitamin D level of ≥ 20 ng/mL and ≤ 40 ng/mL at screening will receive an initial loading dose of 50 000 to 60 000 IU of vitamin D after randomization, preferably by the oral route. Subjects with a serum 25 (OH) vitamin D level of > 40 ng/mL at screening may also receive the vitamin D loading dose at the principal investigator's discretion.

6.2.2.3 Non-Amgen Non-investigational Products Dose Adjustments

If a subject develops hypercalcemia over the course of the study, the principal investigator may use his/her medical judgment and reduce the calcium and/or vitamin D supplementation to maintain serum calcium concentration within the normal range.

If a subject develops hypocalcemia over the course of the study, appropriate additional supplementation should be instituted as deemed acceptable by local guidelines, to maintain serum calcium concentration within the normal range.

If a subject is unable to tolerate the daily calcium or vitamin D supplementation, the formulation may be changed or the dosage lowered. The intolerance as well as the resolution (ie, change in formulation or dosage) should be documented in the subject chart.

6.3 Hepatotoxicity Stopping and Rechallenge Rules

Subjects with abnormal hepatic laboratory values (ie, alkaline phosphatase [ALP], aspartate aminotransferase [AST], alanine aminotransferase [ALT], total bilirubin [TBL]) and/or international normalized ratio [INR] and/or signs/symptoms of hepatitis (as described below) may meet the criteria for withholding or permanent discontinuation of Amgen IP or other protocol-required therapies as specified in the [Guidance for Industry Drug-Induced Liver Injury \(DILI\): Premarketing Clinical Evaluation, July 2009](#)).

6.3.1 Criteria for Permanent Discontinuation of Amgen Investigational Product and Other Protocol-required Therapies due to Potential Hepatotoxicity

Amgen IP (romosozumab/placebo) should be discontinued permanently and the subject should be followed according to the recommendations in [Appendix A](#) (Additional Safety Assessment Information) for possible DILI, if ALL of the criteria below are met:

- TBL > 2x ULN or INR > 1.5
- AND increased AST or ALT from the relevant baseline value as specified below:

Baseline AST or ALT value	AST or ALT elevation
< ULN	> 3x ULN

- AND no other cause for the combination of the above laboratory abnormalities is immediately apparent; important alternative causes for elevated AST/ALT and/or TBL values include, but are not limited to:
 - Hepatobiliary tract disease
 - Viral hepatitis (eg, Hepatitis A/B/C/D/E, Epstein-Barr Virus, cytomegalovirus, Herpes Simplex Virus, Varicella, toxoplasmosis, and Parvovirus)

- Right sided heart failure, hypotension or any cause of hypoxia to the liver causing ischemia
- Exposure to hepatotoxic agents/drugs or hepatotoxins, including herbal and dietary supplements, plants and mushrooms
- Heritable disorders causing impaired glucuronidation (eg, Gilbert’s Syndrome, Crigler-Najjar syndrome) and drugs that inhibit bilirubin glucuronidation (eg, indinavir, atazanavir)
- Alpha-one antitrypsin deficiency
- Alcoholic hepatitis
- Autoimmune hepatitis
- Wilson’s disease and hemochromatosis
- Nonalcoholic Fatty Liver Disease including Steatohepatitis
- Non-hepatic causes (eg, rhabdomyolysis, hemolysis)

6.3.2 Criteria for Conditional Withholding of Amgen Investigational Product and Other Protocol-required Therapies due to Potential Hepatotoxicity

For subjects who do not meet the criteria for permanent discontinuation of Amgen IP outlined above and have no underlying liver disease, and eligibility criteria requiring normal transaminases and TBL at baseline or subjects with underlying liver disease and baseline abnormal transaminases, the following rules are recommended for withholding of Amgen IP and other protocol-required therapies:

- Elevation of either AST or ALT according to the following schedule:

Baseline AST or ALT value	AST or ALT elevation
Any	> 8x ULN at any time
Any	> 5x ULN but < 8x ULN for ≥ 2 weeks
Any	> 5x ULN but < 8x ULN and unable to adhere to enhanced monitoring schedule
Any	> 3x ULN with clinical signs or symptoms that are consistent with hepatitis (such as right upper quadrant pain/tenderness, fever, nausea, vomiting, jaundice).

- OR: TBL > 3x ULN at any time
- OR: ALP > 8x ULN at any time

Romosozumab/placebo should be withheld pending investigation into alternative causes of DILI. If IP(s) is withheld, the subject is to be followed according to recommendations in [Appendix A](#) for possible DILI. Rechallenge may be considered if an alternative cause for impaired liver tests (ALT, AST, ALP) and/or elevated TBL, is discovered and the laboratory abnormalities resolve to normal or baseline ([Section 6.3.3](#)).

6.3.3 Criteria for Rechallenge of Amgen Investigational Product and Other Protocol-required Therapies After Potential Hepatotoxicity

The decision to rechallenge the subject should be discussed and agreed upon unanimously by the subject, investigator, and Amgen.

If signs or symptoms recur with rechallenge, then romosozumab/placebo should be permanently discontinued. Subjects who clearly meet the criteria for permanent discontinuation (as described in [Section 6.3.1](#)) should never be rechallenged.

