4.1.2 Exclusion Criteria

- 201 Currently receiving treatment in another investigational device or drug study, or less than 30 days since ending treatment on another investigational device or drug study(ies). Other investigational procedures while participating in this study are excluded.
- 202 Subject has known sensitivity to any of the products to be administered during dosing (calcium supplements, vitamin D products, or mammalian cell derived products).
- 203 Subject likely to not be available to complete all protocol required study visits or procedures, and/or to comply with all required study procedures to the best of the subject and investigator's knowledge.
- 204 History or evidence of any other clinically significant disorder, condition or disease (with the exception of those outlined above) that, in the opinion of the investigator or Amgen physician, if consulted, would pose a risk to subject safety or interfere with the study evaluation, procedures, or completion.
- 205 Subject is pregnant or breastfeeding or is planning to become pregnant or planning to breastfeed during treatment and within 3 months after the last dose of IP.
- 206 BMD T-score ≤ -4.0 at the lumbar spine, total hip, or femoral neck, as assessed by the central imaging vendor at the time of screening, based on DXA scans and using data for Caucasian women from the NHANES 1998.

-
- 207 History of hip fracture.
- 208 History of metabolic or bone disease (except osteoporosis) that may interfere with the interpretation of the results, such as sclerosteosis, Paget's disease, rheumatoid arthritis, osteomalacia, osteogenesis imperfecta, osteopetrosis, ankylosing spondylitis, Cushing's disease, hyperprolactinemia, and malabsorption syndrome.
- 209 Subject with reported history of hearing loss associated with cranial nerve VIII compression due to excessive bone growth (eg, as seen in conditions such as Paget's disease, sclerosteosis, and osteopetrosis).
- 210 History of solid organ or bone marrow transplant.
- 211 History of osteonecrosis of the jaw and/or atypical femoral fracture.
- 212 Vitamin D insufficiency (defined as 25 (OH) vitamin D levels < 20 ng/mL as determined by the central laboratory). Vitamin D repletion will be permitted and subjects may be rescreened.

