- 213 Current, uncontrolled hyper- or hypothyroidism, Uncontrolled hyperthyroidism is defined as thyroid stimulating hormone (TSH) and thyroxine (T4) outside the normal range. Uncontrolled hypothyroidism is defined as TSH > 10.
- 214 Current, uncontrolled hyperparathyroidism or history of hypoparathyroidism, per subject report or chart review. Uncontrolled hyperparathyroidism is defined as: parathyroid hormone (PTH) outside the normal range in subjects with concurrent hypercalcemia; or PTH values > 20% above the upper limit of normal (ULN) in normocalcemic subjects.
- 215 Current hyper- or hypocalcemia, defined as albumin-adjusted serum calcium outside the normal range, as assessed by the central laboratory. Albumin-adjusted serum calcium levels may be retested once in case of an elevated albumin-adjusted serum calcium level within 1.1 x the ULN as assessed by the central laboratory.
- 216 Subject previously has entered this study or has previously participated in a study with a sclerostin antibody product.
- 217 Malignancy within the last 5 years, except non-melanoma skin cancers, cervical or breast ductal carcinoma in situ.
- 218 Possible diagnosis of multiple myeloma or related lymphoproliferative disorder, as assessed by serum protein electrophoresis performed by the local laboratory (electrophoresis results within 6 months of signing consent will be acceptable).
- 221 Positive results for human immunodeficiency virus, per subject report or chart review.
- 222 Use of oral bisphosphonates:
- any dose received within 3 months prior to randomization
 - more than 1 month of cumulative use between 3 and 12 months prior to randomization
 - more than 3 years of cumulative use, unless last dose received \geq 5 years prior to randomization

- 223 Use of intravenous (IV) bisphosphonates
 - Zoledronic acid:
 - any dose received within 3 years prior to randomization
 - more than 1 dose received within 5 years prior to randomization
 - IV ibandronate, IV pamidronate, or IV alendronate:
 - any dose received within 12 months prior to randomization
 - more than 3 years of cumulative use, unless last dose received \geq 5 years prior to randomization
- 224 Use of teriparatide or any PTH analogs:
 - any dose received within 3 months prior to randomization
 - more than 1 month of cumulative use between 3 and 12 months prior to randomization
- 225 Use of strontium ranelate, or fluoride (for osteoporosis):

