 - more than 1 month of cumulative use within 5 years prior to randomization
- 226 Use of denosumab or any cathepsin K inhibitor, such as odanacatib (MK-0822):
 - any dose received within 18 months prior to randomization
- 227 Use of tibolone, cinacalcet or calcitonin:
 - any dose received within 3 months prior to randomization
- 228 Use of systemic oral or transdermal estrogen or selective estrogen receptor modulators (SERMs):
 - more than 1 month of cumulative use within 6 months prior to randomization
- 229 Use of activated vitamin D3, vitamin K2, more than 1 month of cumulative use within 6 months prior to randomization
- 230 Use of hormonal ablation therapy:
 - more than 1 month of cumulative use within 6 months prior to randomization
- 231 Use of systemic glucocorticosteroids: \geq 5 mg prednisone equivalent per day for more than 14 days within 3 months prior to randomization
- 232 Evidence of acute or chronic hepatitis B or hepatitis C virus. Hepatitis status will be evaluated by testing for hepatitis B surface antigen (HepBsAg), total hepatitis B core antibody (HepBcAb) and hepatitis C antibody by the central laboratory at initial screening. Polymerase chain reaction (PCR) should be performed to confirm active disease only if total HepBcAb is positive and HepBsAg is negative or if C antibody is positive.

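### The ±2-week dosing rule sets no minimum interval between 210 mg doses; secondarily, the 6.3.1 hepatic stop appears to have no AST/ALT criterion when both enzymes start at or above ULN

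*Protocol*

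**What the plan says.** **Dose timing.** Protocol 6.2.1.1 schedules six doses: day 1 and months 1 to 5. Section 7.2.3 counts every target date from day 1 in calendar months and does not move later targets when a visit slips. Table 1 gives months 1 to 5 a window of ±7 days. Section 6.2.1.2 asks sites to try to dose inside those windows. For an out-of-window visit it accepts a dose up to two weeks either side of the target, and beyond that the dose counts as missed. The only limit is distance from the target. Neither the protocol nor the SAP limits the distance from the previous dose.

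**Hepatic stop.** Protocol 6.3.1 says IP should be stopped permanently when three limbs hold together: TBL > 2x ULN or INR > 1.5; "AND increased AST or ALT from the relevant baseline value as specified below"; and "no other cause for the combination of the above laboratory abnormalities is immediately apparent". The table for the second limb has one row: baseline < ULN, on-study value > 3x ULN.

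Section 6.3.2 recommends withholding at other thresholds, and its table gives the baseline as *Any* in every row. Its lead-in names two groups: subjects without liver disease under "eligibility criteria requiring normal transaminases and TBL at baseline", and "subjects with underlying liver disease and baseline abnormal transaminases". Section 6.3.3 adds that subjects who clearly meet 6.3.1 "should never be rechallenged".

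No listed criterion in 4.1.2 sets an AST, ALT or TBL limit. Exclusion 204 is a judgement about disorders that "would pose a risk to subject safety or interfere with the study evaluation, procedures, or completion", and 232 covers "Evidence of acute or chronic hepatitis B or hepatitis C virus". The list passes from 218 to 221 ("Positive results for human immunodeficiency virus, per subject report or chart review"); 219 and 220 do not appear in the public text.

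**The concern.** **Dose timing.** Because targets do not shift, a late dose moves closer to the next one, and ±2 weeks on both sides uses up nearly the whole month. A site could follow 6.2.1.2 exactly and still give two full doses within days of each other. Section 6.2.1.1 says that the largest safe single dose has not been determined.

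**Hepatic stop.** A stopping rule exists so that the decision does not depend on how a site reads it. If no row applies, the enzyme limb cannot be met, so 6.3.1 cannot be met. The rechallenge bar in 6.3.3 and the automatic serious-event report in Appendix A both refer back to those criteria. SAP 10.7.2 defines Hy's law laboratory criteria (AST or ALT > 3x ULN, TBL > 2x ULN, ALP < 2x ULN) with no baseline condition. The analysis could therefore flag a subject whom the dosing rule let continue.

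**Working it through.** The plan states no figure on either point, so there is nothing to reproduce first.

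**1. Shortest interval between doses.** Inputs: calendar-month targets (7.2.3), so consecutive targets are g = 28 to 31 days apart; out-of-window latitude 14 days (6.2.1.2); routine window 7 days (Table 1); day 1 is fixed by definition.

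| Sequence | Formula | Shortest interval |
|---|---|---|
| Day 1, then month 1 at −14 | g − 14 | 14–17 days |
| Months 1–5: +14, then −14 | g − 28 | 0–3 days |
| Months 1–5: +14, then in-window −7 | g − 21 | 7–10 days |
| Months 1–5: routine ±7 windows only | g − 14 | 14–17 days |

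Five intervals separate the six doses, and the 0–3 day result applies to four of them. Taking every day-1 date from 2015 to 2019 gives 1,826 × 4 = 7,304 such intervals. The worst case is 3 days in 4,240, 2 days in 2,462, 1 day in 232 and 0 days in 370. So it is 2 or 3 days in 6,702 of 7,304 (92%). These are counts of calendar possibilities, not of expected events.

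Dose context: two doses total 420 mg. Section 6.2.1.1 reports 10 mg/kg SC as the highest single dose tested, and 420 / 10 = 42 kg. At 42 kg or more, even two doses on one day would not exceed it.

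**2. Effect of a 14-day floor.** The latest permitted previous dose is its target + 14. The floor then opens dosing at that target + 28, which is g − 28 = 0 to 3 days before the next target. Dosing closes at the next target + 14. Permitted days are (g − 28) + 1 + 14 = 15 to 18, so the target date is never excluded. The floor does not bind inside the routine windows. Before an in-window dose at −7, it binds only if the previous dose was at least 8 days late (g = 28) or 11 days late (g = 31).

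**3. Hepatic rules on example cases.** Values are multiples of ULN, with ALP 1.2, no hepatitis symptoms and no other apparent cause. *Pooled* means that one enzyme below ULN at baseline lets either enzyme qualify; *by enzyme* means that the rising enzyme itself must have started below ULN.

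| Baseline AST/ALT | On study AST/ALT | TBL | 6.3.1 pooled | 6.3.1 by enzyme | 6.3.2 withhold |
|---|---|---|---|---|---|
| 1.2/1.2 | 3.5/4 | 2.5 | no | no | no |
| 0.8/1.2 | 3.5/4 | 2.5 | stop | stop | no |
| 0.8/1.2 | 2.5/4 | 2.5 | stop | no | no |

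The first case fails on either reading. It is not withheld because 6.3.2 needs AST or ALT > 5x (sustained for 2 weeks, or with enhanced monitoring not followed), > 8x at any time, > 3x with symptoms, TBL > 3x or ALP > 8x. It does meet the SAP 10.7.2 laboratory criteria.

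**4. When the rule could act.** Scheduled chemistry after day 1 is at months 1, 3 and 6, and the last dose is at month 5. If results return after that visit's dose, month 1 bears on four doses (months 2–5), month 3 on two (months 4–5) and month 6 on none.

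**5. A possible new row.** Threshold = max(3, factor × baseline), in multiples of ULN.

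| Baseline | Factor 1.5 | Factor 2.0 |
|---|---|---|
| 1.5 | 3 | 3 |
| 2.0 | 3 | 4 |
| 2.5 | 3.75 | 5 |
| 2.9 | 4.35 | 5.8 |

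At factor 1.5 the 3x threshold holds up to baseline 2.0x, and over that range both readings of the header agree. A rise from 2.9x to 4.0x with TBL 2.5x is still missed, since 4.0 < 4.35, and it is not withheld either.

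**The case against.** **On dosing.** The ±2 weeks is a fallback after every attempt to keep the window. Reaching 0–3 days needs the latest permitted dose followed by the earliest, and a subject who was just late has little reason to come early. Zero days would merge two visits that each have their own assigned box. The IPIM or the IVRS may already enforce spacing. All of this makes the extreme unlikely. It does not change what 6.2.1.2 permits, and the 7–10 day case needs only one late dose and one ordinary early visit. A reader might infer that the plan exposes subjects to an untested dose. The documents do not support that, given the 42 kg figure.

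**On the hepatic stop.** The public text may be incomplete. A baseline column with one category is odd, a row may have been lost in reading the PDF, and 219 or 220 may be the enzyme limit that the 6.3.2 lead-in refers to. This stands, and it makes the point conditional. The failing case is also narrow: bilirubin above 2x ULN without jaundice, and none of the listed alternative causes apparent, although fatty liver or biliary disease could explain raised enzymes at entry.

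A reader might infer that a mandatory stop is broken, or that these subjects are unprotected. Neither follows. The wording is *should*. At any baseline, AST or ALT > 3x ULN brings close observation under Appendix A, with repeat tests within 24 hours, a search for other causes and a hepatology consult. Section 9.1.3 names liver injury as a possible serious event, and investigator judgement remains.

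**Conclusion.** The dosing point holds as a cheap safety improvement. As written, 6.2.1.2 with 7.2.3 permits 0–3 days between doses from month 1 onward in the worst case and 7–10 days in a milder one. Neither document sets a floor, and the IPIM and IVRS could not be checked.

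The hepatic point holds only if the source protocol has no second table row and items 219/220 set no AST/ALT limit. On that assumption, consider a subject with both enzymes at or above ULN at baseline and, on study, AST/ALT > 3x to 5x ULN, TBL > 2x to 3x ULN, no symptoms and no apparent cause. She is neither stopped nor withheld, though she is closely observed. The documents give no baseline enzyme distribution, so the number of such subjects cannot be estimated; a case is unlikely.

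Both are minor. Neither touches the BMD endpoints or the efficacy conclusions.

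**What to change.** 1. **Protocol 6.2.1.2.** After the missed-dose sentence, add: *No dose is to be given less than 14 days after the previous dose.* Fourteen days is the shortest interval the routine windows already allow; it is not a pharmacological limit taken from the documents. The cost is a few early dates lost after a late dose.
2. **Protocol 6.3.1, after checking the source table and items 219/220.** If neither closes the gap, add a row for baseline ≥ ULN: > 3x ULN and at least a stated multiple of baseline. The 3x anchor matches 6.3.1 and SAP 10.7.2. The documents give no rise factor, so the clinical team must choose it, knowing that 1.5 keeps the 3x threshold for baselines up to 2.0x ULN but does not cover all higher ones.
3. **Protocol 6.3.2 lead-in.** Replace the description of the two groups with *whatever their baseline AST, ALT or TBL*, to agree with the table's *Any*.

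The cost is one amendment with up to three text edits and one clinical decision. It adds no visits, procedures or subjects. Appendix A and SAP 10.7.2 can stay as they are.
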